While there have been some case reports using mTOR inhibitors for advanced AMLs^{3,4}, there have been no prospective trials assessing outcomes and growth inhibition in sporadic AMLs in non-tuberous sclerosis populations. Here we propose to investigate the use of everolimus in a population of patients with sporadic AMLs who would otherwise be advised to undergo surgical or percutaneous intervention.

1.2. **Agent under Investigation**

Everolimus is a derivative of rapamycin which acts as a signal transduction inhibitor. Everolimus selectively inhibits mTOR (mammalian target of rapamycin), specifically targeting the mTOR-raptor signal transduction complex. mTOR is a key serine-threonine kinase in the PI3K/AKT signaling cascade, which is known to be dysregulated in a wide spectrum of human cancers⁵.

Everolimus is being investigated as an antitumoral agent based on its potential to act directly on the tumor cells by inhibiting tumor cell growth and proliferation and indirectly by inhibiting angiogenesis leading to reduced tumor vascularity (via potent inhibition of tumor cell VEGF (vascular endothelial growth factor) production and VEGF-induced proliferation of endothelial cells).

1.3. mTOR pathway and cancer

At the cellular and molecular level, everolimus acts as a signal transduction inhibitor. It selectively inhibits mTOR, a key protein kinase which regulates cell growth, proliferation and survival. The mTOR kinase is mainly activated via the phosphatidylinositol 3-kinase (PI3-Kinase) pathway through AKT/PKB and the tuberous sclerosis complex (TSC1/2). Mutations in these components or in PTEN, a negative regulator of PI3-kinase, may result in their dysregulation. Abnormal functioning of various components of the signaling pathways contributes to the pathophysiology of numerous human tumors, including AMLs. Various preclinical models have confirmed the role of this pathway in tumor development.

The main known functions of mTOR include the following⁶:

- mTOR functions as a sensor of mitogens, growth factors and energy and nutrient levels
- Facilitating cell-cycle progression from G1-S phase in appropriate growth conditions
- The PI3K/mTOR pathway itself is frequently dysregulated in many human cancers, and oncogenic transformation may sensitize tumor cells to mTOR inhibitors
- PI3-kinase mutations have been reported in the primary tumor in 10-20% of human colorectal cancers⁷
- The loss of PTEN protein, either through gene deletion or functional silencing (promoter hypermethylation), is reported in approximately 60% of primary human colorectal cancers⁸
- The mTOR pathway is involved in the production of pro-angiogenic factors (i.e., VEGF) and inhibition of endothelial cell growth and proliferation
- Through inactivating eukaryotic initiation factor 4E binding proteins and activating the 40S ribosomal S6 kinases (i.e., p70S6K1), mTOR regulates protein translation, including the HIF-1 proteins. Inhibition of mTOR is expected to lead to decreased expression of HIF-1

1.4. Non-clinical experience

Everolimus inhibits the proliferation of a range of human tumor cell lines in vitro including cell lines originating from lung, breast, prostate, colon, melanoma, and glioblastoma. IC50s range from sub/low nM to μ M. Everolimus also inhibits the

proliferation of human umbilical vein endothelial cells (HUVECS) in vitro, with particular potency against VEGF-induced proliferation suggesting that everolimus may also act as an anti-angiogenic agent. The anti-angiogenic activity of everolimus was confirmed in vivo. Everolimus selectively inhibited VEGF-dependent angiogenic response at well tolerated doses. Mice with primary and metastatic tumors treated with everolimus showed a significant reduction in blood vessel density when compared to controls.

The potential of everolimus as an anti-cancer agent was shown in rodent models. Everolimus is orally bioavailable, residing longer in tumor tissue than in plasma in a subcutaneous mouse xenograft model, and demonstrating high tumor penetration in a rat pancreatic tumor model. The pharmacokinetic profile of everolimus indicates sufficient tumor penetration, above that needed to inhibit the proliferation of endothelial cells and tumor cell lines deemed sensitive to everolimus in vitro.

Everolimus administered orally daily was a potent inhibitor of tumor growth, at well tolerated doses, in 11 different mouse xenograft models (including pancreatic, colon, epididymoid, lung and melanoma) and two syngeneic models (rat pancreatic, mouse orthotopic melanoma). These models included tumor lines considered sensitive and “relatively resistant” in vitro. In general, everolimus was better tolerated in mouse xenograft models than standard cytotoxic agents (i.e., doxorubicin and 5-fluorouracil), while possessing similar anti-tumor activity. Additionally, activity in a VEGF-impregnated subcutaneous implant model of angiogenesis and reduced vascularity (vessel density) of everolimus-treated tumors (murine melanoma) provided evidence of in vivo effects of angiogenesis.

It is not clear which molecular determinants predict responsiveness of tumor cells to everolimus. Molecular analysis has revealed that relative sensitivity to everolimus in vitro correlates with the degree of phosphorylation (activation) of the AKT/PKB protein kinase and the S6 ribosomal protein; in some cases (i.e., glioblastoma) there is also a correlation with PTEN status.

In vivo studies investigating the anti-tumor activity of everolimus in experimental animal tumor models showed that everolimus monotherapy typically reduced tumor cell growth rates rather than produced regressions. These effects occurred within the dose range of 2.5 mg to 10 mg/kg, orally once a day.

In preclinical models, the administration of everolimus is associated with reduction of protein phosphorylation in target proteins downstream of mTOR, notably phosphorylated S6 (p-S6) and p-4E-BP1, and occasionally with an increase in phosphorylated AKT, a protein upstream of mTOR signaling pathway.

All significant adverse events observed in toxicology studies with everolimus in mice, rats, monkeys and mini-pigs were consistent with its anticipated pharmacological action as an anti-proliferative and immunosuppressant and at least in part reversible after a 2 or

4-week recovery period with the exception of the changes in male reproductive organs, most notably testes.

These data provoke inquiry into the far more common clinical scenario of patients with sporadic AMLs¹¹¹²¹³¹⁴. Although comparatively robust literature does not exist for sporadic AMLs, preclinical data seems to indicate that aberrant mTOR signaling is equally prevalent in sporadic AMLs¹⁵. Kenerson et al examined the activity of this pathway in sporadic AMLs and PEComas using immunohistochemical and biochemical analyses and report increased levels of phospho-p70S6K, a marker of mTOR activity, in 15 of 15 sporadic AMLs¹⁵. This finding was accompanied by reduced phospho-AKT expression suggesting disruption of TSC1/2 function. In their study Western blot analysis confirmed mTOR activation concurrent with the loss of TSC2 and not TSC1 in sporadic AMLs. Similarly, elevated phospho-p70S6K and reduced phospho-AKT expression was detected in 14 of 15 cases. Taken together, these observations provide functional evidence that mTOR activation is common to sporadic, non-TSC-related AMLs and suggest the possibility that mTOR inhibitors such as everolimus may be therapeutic for non-hereditary AMLs.

Here we hypothesize that inhibition of the mTOR pathway may be an effective therapeutic strategy in patients with sporadic AMLs. While EXIST-2 data demonstrate mTOR inhibition is unlikely to induce a complete response with disappearance of the

lesions, they do suggest a role for mTOR inhibitors in “resetting the biological clock” by decreasing tumor volume and thereby decreasing or delaying the risks/need for intervention. The strategy of resetting the “biological clock” has evolved from the collective experience with surgically managing renal tumors in patients with Von Hippel-Lindau (VHL) where this strategy is now considered the standard of care in the absence of curative interventions¹⁶. In the context of AMLs, resetting the biological clock suggests the ability to reduce the size of the tumor to <3cm and potentially reset future growth rates to delay or avoid the need for intervention.

Given the above considerations, herein we seek to study the role of everolimus in (1) reducing the size/volume of clinically significant sporadic AMLs (>3cm) (2) quantitating re-growth upon discontinuation of the agent and (3) minimizing symptoms and the need for intervention within 12 months following discontinuation.

2.0 Objectives

2.1. Primary Objective

- 1) To evaluate the efficacy and tolerability of everolimus in reducing tumor volume in sporadic AMLs as measured by dynamic contrast enhanced MRI (DCE MRI), in patients who might otherwise be considered for active surgical or percutaneous intervention.

2.2. Secondary Objectives

- 1) To evaluate health-related quality of life (HRQoL) in subjects treated with everolimus for sporadic AMLs.
- 2) To assess the growth kinetics of sporadic AMLs in patients who have been treated with everolimus.
- 3) To measure the rate of surgical or percutaneous (embolization) intervention at 1 year from day 1 of study.
- 4) To assess the safety of everolimus in patients with sporadic AML.

2.3. Exploratory Objectives

- 1) To determine whether volumetric response rates in sporadic AMLs to everolimus qualitatively correspond to perfusion/angiogenic content/vascularity of baseline tumor as measured by qualitative DCE MRI using the principles of Choi response criteria (AUC for first 30 seconds post injection).
- 2) To investigate and explore potential molecular mechanism(s) of response and/or resistance of sporadic AMLs to everolimus treatment using a) initial diagnostic tumor tissue samples and if a biopsy or tumor resection is clinically indicated and pursued that tumor tissue sample and b) serum cfDNA.

3.0 Study Plan

After confirming eligibility criteria, patients will be enrolled in this study. Volumetric and perfusion/vascularity analyses will be done by DCE-MRI at baseline. Patients will then receive everolimus 10 mg daily. Treatment duration will be continuous for 4 cycles unless treatment is discontinued.

After 4 cycles of treatment, repeat imaging with DCE-MRI will be performed to assess tumor size kinetics (sum of volumes of all target AMLs identified at baseline). If the tumor has decreased in size by greater than or equal to 25% and no new AMLs greater than 1 cm in longest diameter have appeared, then the drug will be continued for another two cycles (6 cycles total treatment). If on the other hand the tumor has grown or decreased by less than 25% or there are new AMLs (at least 1 cm in longest diameter), then the drug will be discontinued.

At the end of cycle 6 and 12 months after start of therapy with everolimus, imaging via DCE MRI will be repeated to assess growth/regrowth kinetics/qualitative perfusion.

If for any reason a patient terminates treatment with everolimus earlier than the end of cycle 4, all imaging will still be performed and used for the statistical analysis and primary endpoint calculations. Given that therapy with everolimus has potential toxicity and that the disease in question (sporadic AML) is not a malignant condition, patients will not be replaced if they drop out, in a way signaling that the therapy may not be feasible. If a patient receives at least one dose of everolimus they will be included in the analysis. If a patient does not get imaged after 4 cycles of treatment, for the purposes of statistical considerations they will be considered a non-responder.

Treatment related toxicities and QOL will be assessed at baseline, day 1 of each 28 day cycle, at drug discontinuation and at the last study visit

Tissue for exploratory objectives will be collected at baseline only if available from archival tissue. Additional tissue will also be collected if the patient undergoes a partial or complete nephrectomy or embolization during the study period for the AML. Serum at baseline will also be collected for cfDNA and other future potential correlative studies.

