5.4. **Criteria for Discontinuation**

Patients will be removed from treatment if one of the following criteria applies:

- Disease progression including:
 - Bleeding or pain
 - Requirement for surgical or percutaneous intervention
 - Greater than a 25% increase in tumor volume of AML
- Intercurrent illness that prevents further administration of treatment

- Unacceptable adverse events
- Treatment is temporarily held for > 21 days
- Patient becomes pregnant
- Patient decides to withdraw from the study
- General or specific changes in the patient's condition that render the patient unacceptable for further treatment in the judgment of the investigator.

The reason for discontinuation and the date the patient was removed must be documented in the medical record and case report form.

5.5. **Optional Tissue and Blood Collection for Exploratory Objectives**

At time of trial initiation, patients will be consented to allow the use of their tissue and blood for future research, specifically including, but not limited to, the analysis of mTOR alterations, VEGF pathways and tumor genome sequencing (e.g. mutations (AKT/PI3K, PTEN), amplifications, deletions in TSC1 and TSC2).

At screening, if archival biopsy tissue of the AML is available, unstained slides will be requested. If a patient undergoes a clinical procedure where tissue will be obtained during the study, that tissue will also be collected for exploratory objectives. Biopsy, resection, and/or percutaneous intervention will be performed entirely at the discretion of the treating clinician based on individual clinical scenarios and needs.

An EDTA and red top tube will be collected to provide plasma, serum and peripheral blood mononuclear cells (PBMCs). All biological samples will be stored at Fox Chase Cancer Center for possible future research.

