12.0 Statistical Considerations

12.1. Study Design/Endpoints

The required sample size for this trial is 43 patients, using a Simon two-stage design. The sample size justification and details are below.

We will conduct a single arm Phase II study to assess the efficacy of everolimus in patients with ≥ 3 cm sporadic AMLs. Response for a patient will be defined by a decrease in size of $\geq 25\%$ after 4 cycles of treatment.

We will implement an optimal two-stage Simon design for this trial. The new treatment would be of interest if the proportion, p , of responding patients is at least 25%. A proportion of patients with a response rate of less than 10% will be of no interest. Forty three (43) patients will allow us to test the null hypothesis: $p \leq 10\%$ against the alternative hypothesis: $p \geq 25\%$ at the 5% level of significance (α) with 80% power for a one-sided test. The early stopping point is 18 patients for both efficacy and toxicity. For efficacy, if 2 or fewer patients respond among the first 18 patients then the null hypothesis will not be rejected and the trial will be terminated. The probability of early stopping under the null is 73%. If the trial progresses until 43 patients are evaluated and 8 or more patients respond, then the null hypothesis will be rejected.

For toxicity, the trial will be paused and termination considered if out of the first 18 patients, 3 or more come off trial due to any adverse events as defined in the protocol. If the study proceeds to stage II (total enrollment = 43 patients), the trial will be paused and termination considered if at any point 8 or more patients come off trial due to any adverse events as defined in the protocol. If the true rate of any adverse events necessitating a patient to come off trial is 20%, the probability of early stopping is 73%; if the true rate of any adverse events necessitating a patient to come off trial is 5%, the probability of early stopping is 6%. Pause and

termination consideration for toxicity will occur, either early or finally, with probability 81% if true toxicity proportion is 20%; and 6% if it is 5%.

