To ensure oversight with respect to toxicity, an interim review will be conducted if the early stopping rule for toxicity is reached in the first 18 patients. For this interim review, all available data related to primary and secondary efficacy and toxicity endpoints will be collected, summarized and presented. The data will be reviewed at a meeting of the invested trial parties, including but not limited to investigators at all participating sites (PIs or representatives at outside centers may call in to the meeting), staff on the research team, members of the FCCC Investigator Sponsored Research Unit, and statistics team. A summary recommendation will emerge from the meeting as to whether the study should be terminated or modified to a new dosing schema. This recommendation will be forwarded to the FCCC DSMB for signoff. Study accrual will halt until the outcome of the interim review is accepted by the FCCC DSMB. If the DSMB does not concur with the findings of the Investigator Meeting, the local FCCC IRB will review the trial for final decision.

In secondary analyses we will use graphs, standard descriptive statistics (mean, median, minimum, maximum, standard deviation, two-sided 95% confidence intervals) and Generalized Estimating Equation methods to characterize and model longitudinal health-related quality of life (HRQoL) measurements. Tumor regrowth kinetics will be characterized by the percent change in volume from the date of everolimus treatment termination. Values will be summarized using plots and standard descriptive statistics (mean, median, minimum, maximum, standard deviation, two-sided 95% confidence intervals) separately for each measurement following treatment discontinuation. Safety and tolerability objective will be measured by the incidence of adverse events, serious adverse events, deaths and laboratory abnormalities. Spearman's correlation coefficients will be computed to estimate the association between the largest percentage volumetric response from baseline with levels of perfusion/angiogenic content/vascularity of baseline tumor as measured by DCE MRI.

We will tabulate the frequencies of all grade 2 or higher adverse events as defined by NCI CTCAE version 4 criteria. The criteria are available online at <http://ctep.cancer.gov/reporting/ctc.html>.

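### The scoring rules can count a patient whose target AML was resected or embolized before the Cycle 5 Day 1 MRI as an everolimus responder

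*Combined protocol and SAP*

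**What the plan says.** - **Use of scans after an early stop (3.0 Study Plan).** If everolimus ends before the end of cycle 4 for any reason, "all imaging will still be performed and used for the statistical analysis and primary endpoint calculations". Everyone with at least one dose is analysed, and the measure is the summed volume of the target AMLs identified at baseline.
- **Non-response (3.0).** One situation is expressly scored as non-response: "If a patient does not get imaged after 4 cycles of treatment".
- **Response (12.1 Study Design/Endpoints).** "Response for a patient will be defined by a decrease in size of" at least 25% after 4 cycles. Nothing is said about what produced the decrease.
- **Timing (11.1).** The response MRI is fixed by visit, at Cycle 5 Day 1.
- **Discontinuation (5.4).** Under the entry "Disease progression including", the list contains "Requirement for surgical or percutaneous intervention".
- **Procedures are expected.** Section 2.1 describes the population as "patients who might otherwise be considered for active surgical or percutaneous intervention". Section 3.0 plans tissue collection if a patient "undergoes a partial or complete nephrectomy or embolization during the study period for the AML". Objective 2.2.3 measures the intervention rate at 1 year.
- **Other uses of the volumes (12.1).** Regrowth is summarized as percent change from the end of treatment. The "largest percentage volumetric response from baseline" enters a Spearman correlation with baseline perfusion. Neither analysis mentions procedures.

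**The concern.** No sentence calls an operated patient a responder. The result comes from applying the rules together. A patient who has the target AML resected in cycle 2 stops everolimus early, is still imaged at Cycle 5 Day 1, and shows a summed target volume well over 25% lower. If it was the only target, the decrease is 100%. The patient was imaged, so the non-responder rule does not apply, and the definition in 12.1 is met. Embolization, or treatment of one of several targets, gives the same result if the sum falls by at least 25%.

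The error favours the drug. Section 1.5 presents everolimus as a way to delay or avoid intervention, so a failure of that aim would be recorded as a success. The trial is single-arm with small cut-offs, and no control group would reveal the misclassification.

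**Working it through.** **Inputs (12.1).** Null response 10%, alternative 25%; n1 = 18, stop at 2 or fewer responses; N = 43, reject at 8 or more; one-sided alpha 5%, power 80%, early stopping under the null 73%.

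**Formula.** With X1 ~ Bin(18, p) and X2 ~ Bin(25, p):

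- P(stop) = P(X1 ≤ 2)
- P(reject) = Σ over x = 3 to 18 of P(X1 = x) · P(X2 ≥ 8 − x)

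**Plan's own figures.** At p = 0.10, P(stop) = 0.7338 and P(reject) = 0.0480. At p = 0.25, P(reject) = 0.8003. The stated design is reproduced.

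**Effect by count.** Fix the affected patients as responders and leave the others at 10%.

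- One in stage 1: type I error 0.1093, and P(stop) falls from 0.734 to 0.482. One in stage 2: type I error 0.0879.
- One placed at random: (18/43)(0.1093) + (25/43)(0.0879) = 0.097.
- Two placed at random: both in stage 1 gives 0.2166, one in each stage 0.1913, both in stage 2 0.1428. Weights are 306/1806, 900/1806 and 600/1806, so the result is 0.179.

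**Effect by rate.** Let q be the share of patients with a procedure on a target AML before the Cycle 5 Day 1 MRI, independent of drug response. The documents give no value, so q is an assumption. Suppose all are imaged and all reach the 25% cut. The scored response rate at a 10% drug rate is then 0.10(1 − q) + q = 0.10 + 0.90q. If only half reach the cut, it is taken as 0.10 + 0.45q.

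| q | Scored rate (all count) | P(stop) | Type I error (all count) | Type I error (half count) |
|---|---|---|---|---|
| 0 | 0.100 | 0.734 | 0.048 | 0.048 |
| 1% | 0.109 | 0.688 | 0.072 | 0.059 |
| 2% | 0.118 | 0.641 | 0.103 | 0.072 |
| 5% | 0.145 | 0.504 | 0.230 | 0.120 |

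At q = 1% the chance of at least one such patient in 43 is 1 − 0.99^43 = 0.35.

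**A rough anchor.** The only related figure is in 1.5: 89.4% progression-free at 36 months in the randomized everolimus trial in TSC/LAM. At a constant hazard over 16 weeks (3.68 months), 1 − exp[(ln 0.894 / 36) × 3.68] = 0.0114. It describes progression, not intervention, in a different treated population, so it is illustrative only.

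**After the fix.** Scoring these patients as non-responders makes the rate p(1 − q).

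| q | Type I error (p = 0.10) | Power (p = 0.25) |
|---|---|---|
| 1% | 0.0457 | 0.7914 |
| 2% | 0.0435 | 0.7822 |
| 5% | 0.0373 | 0.7526 |

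**The case against.** The strongest reply is that 12.1, the response criteria in 11.3 and the non-responder sentence in 3.0 all tie response to 4 cycles of treatment. A patient operated on in cycle 2 has not had 4 cycles, so could be held a non-responder, and using a scan in the calculations does not settle how the patient is scored. This reading is possible, but it leaves the 3.0 sentence on early stoppers' imaging with little purpose, and 11.1 fixes the scan by visit. The text at least permits the wrong score, and the choice should not be left until data are seen.

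Second, 5.4 governs removal from treatment, and no endpoint in section 12 uses progression. That is correct. The mismatch with 5.4 shows how the protocol regards intervention, but the scoring gap exists without it. It also stands that 5.4 speaks of requiring an intervention, whereas the rule below covers only procedures performed; a patient still awaiting one has a volume that no procedure has altered.

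Third, the size is assumed. At the 1.1% anchor, type I error would be 0.076, or 0.061 if half of procedures reach the cut, and there is a 61% chance that no such patient occurs. This stands, and q = 5% should be read as a stress case.

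Finally, the regrowth and correlation analyses are descriptive or exploratory. That part is minor.

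**Conclusion.** The concern holds. As written, sections 3.0 and 12.1 can score the result of surgery or embolization as an everolimus response. The sample size and stopping rules themselves are correct.

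The consequence is conditional. With no procedure on a target AML before the Cycle 5 Day 1 MRI, nothing changes. With one or two counted as responses, the type I error roughly doubles or nearly quadruples against the stated 5% design. These figures assume a 10% response rate among the other patients and that the affected patients are imaged, reach the 25% decrease and are scored literally. The sponsor should fix this before the response data are examined; confidence is medium, because the intervention rate is unknown and the wording allows another reading.

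**What to change.** Add to 3.0 and 12.1:

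> For endpoint scoring only, a patient who has surgery or embolization of a target AML before the Cycle 5 Day 1 MRI is a non-responder, whatever the volume on that MRI. Treatment and imaging are unchanged.

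Add to 12.1:

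> Volumes measured after a procedure on a target AML are flagged, and the regrowth summaries and the largest percentage response are reported with and without them.

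Reporting both ways is better than deleting these volumes, because patients who need a procedure may be those with the fastest regrowth.

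The text change is three sentences, and procedure dates are already needed for objective 2.2.3. Type I error stays at or below 0.048. The cost is power: the design has none to spare at 0.8003, and the rule can only keep the response rate the same or lower it. A patient whose targets shrank on drug but who had one of several treated would also count as a non-responder. The sponsor should accept that loss knowingly.
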